		7.1.1 Study design	
		7.1.2 Personnel qualifications	
		7.1.3 Reports and Archiving of Study Documentation	27
		7.1.4 Statistical Analysis	27
	7.2	Audit from Quality Assurance Unit	27
	7.3	Data Management	27
8	Statist	tical Methods and Determination of Sample Size	28
	8.1	General Aspects	28
	8.2	Analysis set	
	8.3	Statistical Methods	
	8.4	Interim Analyses	28
	8.5	Determination of Sample Size	
9	Repor	ts and Archiving of Study Documentation	
		•	

Intensive Drug Monitoring Protocol

Version: 1.0 Date: 11-May-2020

10	References	.30
11	Appendices	. 31

Date: 11-May-2020

Study summary

International Nonproprietary Name:	Brand name:
Degarelix Acetate for Injection	FIRMAGON®
Formulation and specification:	Compound:
(1)80mg; (2)120mg (Calculated by Degarelix)	Degarelix
Date of first approval in China:	New drug monitoring period:
2018.9.11	2018.9.11-2023.9.10
Date to domestic market:	International Birth Day:
2019.04	2008.12.24
Reason for Monitoring:	Implementation provinces:
Per regulatory authority's requirement of drug	Nationwide
intensive monitoring for all new approval products	
Start Date:	End Date:
Q1 2021	Dec 2022
Financial support:	Total expenditure:
Ferring Pharmaceuticals (Asia) Co.Ltd.	Undetermined
Study Number: 000351	Phase: IV

Sponsor: Ferring Pharmaceuticals (Asia) Co.,Ltd.

Address: [name]

Trade Zone

PPD

Phone Number: [name] **PPD**

Submission of Information:

FIRMAGON® intensive drug monitoring protocol: Version 1.0, 11-May-2020 Plan Protocol submission to national ADR Monitoring Center: June-2020

Objective:

• To evaluate the safety profile of FIRMAGON® (to fulfill the regulatory authority's requirement of Intensive Drug Monitoring in Chinese patients with prostate cancer need androgen deprivation therapy treated with FIRMAGON®)

Outcomes:

• To evaluate safety and tolerability of degarelix one-month dosing regimen in Chinese patients diagnosed with prostate cancer and need Androgen Deprivation Therapy.

Summary of study methods:

Intensive Drug Monitoring Protocol Version: 1.0

Date: 11-May-2020

• Study Design

This study is a multi-center, single-arm, non-interventional, prospective study among Chinese patients with prostate cancer and need androgen deprivation therapy receiving treatment with FIRMAGON®. This program will provide the minimum 6 doses and maximum 12 doses of FIRMAGON® to enrolled patients during one-year follow-up. Patients who meet inclusion criteria and will or are accepting at least 6 self-financed doses treatment in hospital. Patients should return to the hospital for medical assessment every three months. The prescription of 6 (3 dose × 2 times) self-financed doses will be given by doctors after assessment, and the direct-to-patient pharmacy will distribute FIRMAGON® to eligible patients (patients should bring the prescriptions and the last FIRMAGON® boxes to get other doses). All enrolled patients will be followed up to collect safety information for one year from the 1st dose unless withdrawal of Informed Consent Form, discontinuation for 2 months, lost to follow-up, death, or termination due to other reasons, whichever comes first.

• Study sites

Data will be collected by China Primary Healthcare Foundation from patients or Health care providers (HCPs). 138 target hospitals are in the charity support list.

Patients number

2500 patients who are prescribed FIRMAGON® according to clinical practice by doctors in hospitals will be enrolled in this study.

• Main Inclusion Criterion

Patients must meet all the criteria listed below to be eligible for participation in the project.

- > Diagnosis with prostate cancer and need androgen deprivation therapy
- > Decision made to prescribe of FIRMAGON® prior to enrolment.
- Willingness and ability to provide written informed consent.
- The patients are from whom taken post-marketing drug FIRMAGON®.

• Main Exclusion Criterion

Any patient who meets the following criterion will not be qualified for the entry of this study:

- Not sign Informed Consent.
- Any patients who is unsuitable to participate in this study because of any other reasons will not be qualified to participate in this study.
- Data collection

The data below will be collected based on the current clinical practice and no additional data, diagnostic or monitoring procedures are applied to the patients.

Patient demographic information of age

Intensive Drug Monitoring Protocol Version: 1.0

Date: 11-May-2020

- Disease characteristics: PSA and Testosterone
- > Treatment: detail of FIRMAGON®, medical history and concomitant medications
- Adverse events after FIRMAGON® treatment: AE name, start date, end date, severity, serious or non-serious, causality, actions to FIRMAGON®, treatment due to AE, outcome, etc.
- Data management

In this study, all enrolled patient demographic information will be recorded in charity's database. AE data will be filled in Adverse Event Form (as Appendix 1), processing in safety database and submitting to relevant authorities. Data will be regularly checked to ensure the quality.

submitting to relevant authorities. Data will be regularly checked to ensure the quality.

• Study schedule
Planned Start of Study:
Planned the end of the last patient's follow-up:
Planned completion of the Study Report:
Dec 2022

Conclusion of Intensive Drug Monitoring Study:

Remarks:

Intensive Drug Monitoring Protocol

Version: 1.0 Date: 11-May-2020

List of Abbreviations and Definition of Terms

AE Adverse Event

ADR Adverse Drug Reaction

Ferring Pharmaceuticals (Asia) Co., Ltd.

CA Competent Authority

CRO Contract Research Organisation

HCP Health care provider

ICF Informed Consent Form

International Council for Harmonisation of Technical

ICH Requirements for Pharmaceuticals for Human Use

IDM Intensive Drug Monitoring

IEC Independent Ethics Committee

MAH Marketing Authorization Holder

NMPA National Medical Products Administration

GPP Pharmacoepidemiology practice

PSA Prostate specific antigen

PV Pharmacovigilance

SAE Serious Adverse Event

SAP Statistical Analysis Plan

UAT User Acceptance Test

1 Introduction

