1.3 Preliminary safety assessment results

Domestic Clinical Trials

The safety of Degarelix was investigated in a China Phase III active-controlled trial in Chinese patients (N = 283) receiving monthly Degarelix (subcutaneous injection) or Goserelin (subcutaneous injection) for 12 months. Adverse events reported in $\geq 5\%$ patients were showed in Table 1.

Table 1, Adverse Events occurred in >=5% Patients in the Groups by MedDRA System Organ Class and Preferred Term - Safety Analysis Set

	Degarelix 240/80mg	Goserelin 3.6mg
	(S.C.)	(S.C.)
	N=142	N=141
Any Adverse Event	76.1%	58.9%
General Disorder and administration site condition		
Injection site reactions	45.1%	1.4%
Injection Site Swelling	26.8%	0.7%
Injection Site Erythema	26.8%	
Injection Site Pain	24.6%	0.7%
Injection Site Mass	7.0%	
Pyrexia	12.7%	1.4%
Fatigue	5.6%	2.1%
Infections and Infestations		
Urinary tract infection	7.0%	7.8%
Vascular Disorders		
Hypertension	9.9%	10.6%

MedDRA version 18.0

Ferring Pharmaceuticals (Asia) Co., Ltd.

The most common adverse events in patients treated with Degarelix were injection site reactions, including injection swelling (26.8%), injection site erythema (26.8%), injection site pain (24.6%), and injection site mass (7.0%).

Most injection site reactions were mild or moderate in severity (2 patients with severe injection site reactions: 1 with severe injection erythema and 1 with severe injection site mass), and there is no hypersensitivity reaction of immediate onset. Adverse events mainly occurred in the initial stage of treatment, and their incidences were decreased with time. No patients discontinued from the trial due to injection site reactions.

Of abnormalities in hepatic function test, alanine aminotransferase (ALT) (with or without total bilirubin), aspartate aminotransferase (AST), and total bilirubin were comparable between the treatment groups. No patient developed increased ALT considered as serious adverse event, and no patient discontinued from the trial due to increased ALT.

ECG results showed that, there was no significant differences of mean change of QTcF between the treatment groups from baseline to Day 3 and to the end-of-trial visit.

QTcF >=500 msec occurred in 13 patients, including 7 (5%) patients in the Degarelix Group and 6 (4%) patients in the Goserelin Group.

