This study is a multi-center, single-arm, non-interventional study among Chinese patients with prostate cancer needed androgen deprivation therapy receiving treatment with FIRMAGON®. 2500 patients who are prescribed FIRMAGON® according to clinical practice by doctors in hospitals will be enrolled in this study. This program will provide the minimum 6 doses and maximum 12 doses of FIRMAGON® to enrolled patients during one-year follow-up. Patients apply for enrollment in hospital, they will return to hospital every three months for medical assessment and other three doses of FIRMAGON® prescription during the study. 138 target hospitals are in the charity support list. The direct-to-patient pharmacy will distribute FIRMAGON to patients who are defined eligible by the doctor. The patient should bring the prescriptions and the last FIRMAGON® boxes to get other FIRMAGON®.

All enrollment patients will be followed up to collect safety information for one year from China Primary Healthcare Foundation from the 1st dose unless withdrawal of Informed Consent Form, dosing interrupted for 2 months or more than 2 months since last dose, lost to follow-up, death, or termination due to other reasons (defined in section 5.4), whichever comes first. Any AEs will be filled in Adverse Event Form (as Appendices), processing and submitting to relevant authorities.

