5.3 Selection of Study Population

5.3.1 Inclusion Criteria

Patient eligibility is determined according to the following criteria prior to entry into the

study:

1) Diagnosis as prostate cancer and need androgen deprivation therapy

2) Decision made to prescribe of FIRMAGON® prior to enrolment.

3) Willingness and ability to provide written informed consent.

4) The patients are from whom taken post-marketing drug FIRMAGON®.

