5.6 Study Plan

Data collection overview:

Frequency	Inclusion	Every 3 months during total 12 months
Visit Window	The Baseline Visit	The 2nd Visit to the 4th Visit
Obtaining informed consent	X	
Inclusion/Exclusion criteria	X	
Demographic information ¹	X	
Medical history ²	X	
Disease characteristics ³	X	
FIRMAGON® treatment ⁴	X	X
AE collecions ⁵	X	X
Disease condition ⁶	X	X

Definitions:

- 1. Including age and domicile place.
- 2. Including general medical history, surgical history, metastasis situation.
- 3. Prostate cancer: stage, the date of histology diagnosis, Gleason Score, presenting symptoms.
- 4. FIRMAGON® treatment information: initial dose and time, duration, dose adjustment (actions, times and reasons). Details need be collected for permanent withdrawal patients.
- 5. AE name (Verbatim term, SOC, PT), reporter info, event onset date, event stop date, action taken, outcome, seriousness, causality, medical history, concomitant medications.
- 6. Including the level of Serum PSA and Testosterone, and questions about disease progress or remission?

Ferring Pharmaceuticals (Asia) Co., Ltd.

6 Safety Reporting

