6.1 Definitions

6.1.1 Adverse Event

An adverse event (AE) is any untoward medical occurrence in a patient administered a medicinal product and which does not necessarily have to have a causal relationship with this treatment. An AE can therefore be any untoward and unintended sign (including an abnormal laboratory finding), symptom, a new disease or worsening in severity or frequency of a concomitant disease, temporally associated with the use of a medicinal product, whether or not the event is considered causally related to the use of the product. In this study, all AEs (including Serious Adverse Events) after first dose of FIRMAGON® should be collected.

Abnormal laboratory values or outcome of an examination considered as clinically significant by HCP should be reported as an AE.

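### If patients already on FIRMAGON enrol, pooling them with new starters could understate early-onset adverse events by an amount the documents do not let us size

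*Combined protocol and SAP*

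**What the plan says.** **Who may enter.** The Study Design paragraph of the Study summary covers "Patients who meet inclusion criteria and will or are accepting at least 6 self-financed doses treatment in hospital". The sentence is grammatically incomplete, but it names both people about to start and people already on treatment. Inclusion criterion 4 (section 5.3.1) reads "The patients are from whom taken post-marketing drug FIRMAGON", which is worded for people who have already had the drug. Section 5.3.2 has two exclusions, lack of consent and unsuitability for other reasons; neither mentions earlier doses.

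**When observation starts.** Under section 5, patients are "followed up to collect safety information for one year from China Primary Healthcare Foundation from the 1st dose". Section 6.1.1 says "all AEs (including Serious Adverse Events) after first dose of FIRMAGON® should be collected", and section 6.3 also starts collection at the first dose. None of these says whether the dose meant is the first ever or the first in the study. Footnote 4 of section 5.6 records the initial dose and its time, with the same ambiguity. AEs are collected at baseline and then "Every 3 months during total 12 months".

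**How results are reported.** Results are frequencies and percentages of patients without imputation (8.1), all on a single FAS (8.2). Subgroups are to be chosen in the light of who enrols (8.3). Section 7.3 gives off-label patients a separate analysis as well as a place in the overall one; no section does this for earlier exposure.

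**When events occur.** In its paragraph on injection site reactions, section 1.3 says of the China Phase III trial: "Adverse events mainly occurred in the initial stage of treatment, and their incidences were decreased with time".

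**The concern.** Section 5.2 makes AE collection the main purpose of the programme, so the percentage of patients with each event is its principal output. For events that cluster at the start of treatment, that percentage depends on whether the start was observed.

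A new starter begins treatment under follow-up. An ongoing user began before consent, and section 4.3 requires consent before identifiable data are collected. There are then two possibilities:

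- **First-ever dose starts the clock.** His early events are in scope but can only be recovered backwards, from recall or records. No rule says how. A patient enrolled after k months of treatment has about 12 − k months of follow-up left.
- **First in-study dose starts the clock.** His start of treatment lies outside follow-up.

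In both cases his early events may be captured less completely than a new starter's, and a single pooled percentage hides the difference. The most common reaction in the protocol's own table is the one most exposed. Ongoing users are plausible: the drug reached the domestic market in April 2019 and the study starts in Q1 2021.

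**Working it through.** **The plan's own figures.** The sample size of 2500 follows from a discussion with the authority (8.5), so there is no formula to reproduce. Table 1 gives injection site reactions in 45.1% of 142 degarelix patients, which matches 64/142.

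**Inputs.** From the documents: p = 45.1% and N = 2500. Not in the documents, hence assumed:

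- f = share of ongoing users among those enrolled
- e = share of new starters with a reaction who are counted as having one
- c = the same share in ongoing users (a further reaction during follow-up also counts)

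**Formulas.**

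- Pooled incidence = p × [(1 − f)e + fc]
- Part of the shortfall removed by a split = p × f × (e − c)
- Part that stays after a split = p × (1 − e)

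Example, with f = 25%, e = 1, c = 0.5: 45.1 × (0.75 + 0.125) = 39.5%. Removed by a split: 45.1 × 0.25 × 0.5 = 5.6 points.

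| f | e = 1, c = 1 | e = 1, c = 0.5 | e = 1, c = 0 | e = 0.8, c = 0.5 |
|---|---|---|---|---|
| 10% | 45.1% | 42.8% | 40.6% | 34.7% |
| 25% | 45.1% | 39.5% | 33.8% | 32.7% |
| 50% | 45.1% | 33.8% | 22.6% | 29.3% |

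At f = 10 / 25 / 50%, a split removes:

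- e = c: nothing
- e = 1, c = 0.5: 2.3 / 5.6 / 11.3 points, with 0 remaining
- e = 0.8, c = 0.5: 1.4 / 3.4 / 6.8 points, with 45.1 × 0.2 = 9.0 points remaining

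**Against sampling error.** The 95% half-width at 45.1% is 1.96 × √(0.451 × 0.549 / n), which is 1.95 points at n = 2500. With e = 1, the shortfall exceeds this once f(1 − c) > 1.95/45.1 = 4.3%, for example 10% ongoing users with 43% of their reactions missed.

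**Precision after a split.** For patients with no earlier dose, the half-width is 2.25 points at n = 1875 (f = 25%) and 2.76 at n = 1250 (f = 50%).

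**The case against.** **Entry of ongoing users is inferred.** It rests on one incomplete synopsis sentence, which section 5 does not repeat, and on criterion 4, which may only mean that marketed product is used. Read literally, criterion 4 would shut out every new starter. Criterion 2, a decision to prescribe before enrolment, suits people about to start. This stands, so the point must be conditional. A reader might infer that the plan certainly recruits ongoing users, or recruits many; the documents show only that it allows them.

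**Early events are probably in scope.** The most natural reading of sections 6.1.1 and 6.3 is the first dose ever. AEs are collected at baseline, and the AE form has event dates and drug start dates. A reader might infer that the plan discards events before consent; the text does not say so. What remains is that events in scope are not necessarily captured, and no rule covers their recovery.

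**No bias is demonstrated.** f, e and c are assumptions. Section 1.3 gives no rates by month or injection and does not define the initial stage. Injections continue, so ongoing users can still react under observation. New starters face recall over three months too, and in the e = 0.8 example the loss a split cannot remove (9.0 points) exceeds what it removes at every f shown. All of this stands and limits what may be claimed about size.

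**The SAP can add the table later.** Section 8.1 allows finalisation up to a week before database lock, and the study is descriptive. This stands only in part. Doses before consent are not a stated data item, and the initial-dose item can be read two ways. A table added late would rest on data that sites may have recorded inconsistently.

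**Conclusion.** The point holds in conditional form. The plan allows patients already on FIRMAGON to enrol, leaves the first dose undefined, and reports everyone in one FAS without requiring any breakdown by earlier exposure. If such patients enrol and their early events are captured less completely than those of new starters, the pooled incidence of early-onset AEs, chiefly injection site reactions, is understated.

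The amount cannot be derived from the documents. It is zero if capture is equal. In the illustrations with complete capture in new starters and half in ongoing users, it is 2.3 to 11.3 points for 10% to 50% ongoing users. A reader might take one of these as the expected bias; none is, because only the 45.1% comes from the protocol. Nor would the figure for new starters be free of bias, since three-monthly collection can miss events in them as well.

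The change is worth making before enrolment begins, because it depends on an item that must be recorded clearly at entry.

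**What to change.** 1. **Define and record.** In the Study summary, section 5 and footnote 4 of section 5.6, state which dose starts follow-up. Record the date of the first-ever FIRMAGON dose and the number of doses received before consent.
2. **Prespecify the split.** In sections 8.2 and 8.3, keep the pooled FAS for the overall summary and add AE tables by doses before consent (0, 1, 2 or more). State the initiation window. Report initiation-phase incidence mainly in patients with 0 earlier doses, with the 0-or-1 group as a sensitivity analysis: a patient with one earlier dose had his first injection before consent, so those reactions are retrospective. Make 0-or-1 the main set only if criterion 4 is applied so literally that almost nobody has 0.
3. **Flag retrospective events.** Mark AEs with onset before consent, derived from the onset and consent dates, and tabulate them separately.

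**Cost.** Wording changes, one clarified treatment-history item, one more set of tables and a derived flag; no new visits and no exclusions. Intervals for early events widen with the unknown share of ongoing users, as shown in the working. The split does not repair under-capture in new starters.

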1.1 Clinical background

Prostate cancer is one of the most common types of cancer in men. Usually prostate cancer grows slowly and is initially confined to the prostate gland, where it may not cause serious harm. However, while some types of prostate cancer grow slowly and may need minimal or even no treatment, other types are aggressive and can spread quickly. Worldwide, prostate cancer is the second most frequently diagnosed cancer among men with estimated 914,000 new cases (13.8% of total) and 258,000 deaths in 2008. The incidence rate varies more that 25-fold worldwide, highest in Western Europe, Australia & New Zealand and US and lowest in South-Central Asia. The majority of cases occur in developed countries^[6]. The estimated new cases and deaths the Europe in 2008 are 382,300 and 89,300 representing 22.2% of new cancer cases and 9.3% of cancer deaths in men, respectively^[7]. The estimated new cases and deaths in US in 2012 are 241,740 and 28,170, representing 29% of new cancer cases and 9% of cancer deaths respectively^[8]. The variation in incidence rates is also pronounced within Europe with the highest rate in Ireland and the lowest in Greece; age-standardize incidence rates of 183.1 and 31.1 per 100,000, respectively, in 2008. Patterns of mortality rates largely reflect those of incidence rates, but with less variation between countries^[9]. See detail information from risk management plan - RMP for Degarelix (V16.0, 12 Jul 2019).

In recent years, the incidence of prostate cancer has shown an obvious growth trend in China. In 2008, the incidence of prostate cancer of Chinese men was 11.00/100 000, accounting for 3.33% of the incidence of men's malignant tumors; the incidence of urban males was about 3.7 times of that in rural areas; the results of age-specific incidence showed that the incidence of Chinese males over the age of 70 ranked the first place in the males genitourinary tumor; the growth incidence rate of urban men with prostate cancer was 8.53/100 000, higher than 2.53/100 000 in rural areas; the proportion of high age group was increased significantly in the age composition of the incidence over time^[10].

1.2 Medicinal products

FIRMAGON® (Degarelix) is a synthetic linear decapeptide amide containing seven unnatural amino acids, five of which are D-amino acids. FIRMAGON® is a gonadotrophin releasing

Ferring Pharmaceuticals (Asia) Co., Ltd.

hormone (GnRH) antagonist (receptor blocker), and as such blocks the GnRH receptor to induce a rapid decrease in release of LH and FSH from the pituitary, leading to a fast, profound and sustained suppression of testosterone and Prostate specific antigen (PSA) without an initial testosterone surge. No materials used in the synthesis of Degarelix are of human or animal origin.

